14.1 Case report forms

All data from assessments conducted during the study will be recorded on an appropriate case report form (CRF) for each participant. Electronic CRFs will be accessible from the STAREE website. The CRFs must be completed during or after each participant visit (or as soon as all data is available, e.g. once pathology results are obtained) and uploaded onto the STAREE web-based portal. Original hard-copy CRFs and other source documents will be stored in the participant's file at the local study site.

CRFs will be kept current to reflect the participant's course throughout the study. Participants will not be identified on the CRF by name. Appropriately coded identification (GP, Practice and Subject Identification Numbers) and an acrostic of the participant's initials will be used.

The data from the CRFs will be uploaded onto the STAREE web-based data management portal. All information collected will be treated in accordance with professional and ethical guidelines. All corrections and alterations of data on the CRFs must be made according to the instructions provided and must be dated and initialled.

14.2 Data Management

Data collection and management will be centralised at the STAREE data management centre, Department of Epidemiology and Preventive Medicine, Monash University, Melbourne. Study data collected at local study sites will be entered on electronic CRFs with source documentation retained in the participant file. All information related to potential endpoints will be copied from the original documents sourced through clinical notes and hospital medical records and sent de-identified to the STAREE data management centre. Serious adverse event and endpoint data will be accepted as either a) photocopied clinical records or b) scanned or photographed image files of clinical records. The clinic will retain all original information related to the clinical event or endpoint in the subject files.

Electronic study records will be accessible through the internet at the STAREE web-portal. Access to this website will be made available to registered study staff via password protected log-in procedures.

Monash University implements a defence in depth approach to information security and employs a multitude of controls to protect the study's infrastructure and data. These controls are regularly audited to ensure they meet global best practices and are aligned with ISO 27001 security practices. Data collected as part of the STAREE clinical trial will be stored on University managed secure and resilient infrastructure located in Australia that complies with all applicable data protection and privacy obligations. Some specialist data collected as part of the STAREE clinical trial may be entered into applications that are operated by external third parties. This will only be permitted where all applicable data protection and privacy obligations are in place with those external third parties.

Monash University values the privacy of every individual's personal information and is committed to the protection of that information from unauthorised use and disclosure, except where permitted by law. Monash University is subject to and ensures that personal

and health information it holds or has access to, is handled in accordance with data protection and privacy legislation, including the Privacy and Data Protection Act 2014 (Vic) and the Health Records Act 2001 (Vic) and where required, the Privacy Act 1988 (Cth) and applicable international regulations.

14.3 Data analysis

The data will be analysed by statisticians from the Biostatistics Unit, Department of Epidemiology and Preventive Medicine, Monash University.

Baseline characteristics of the two treatment groups will be tabulated and imbalance defined as a 0.25 standard deviation difference in means (quantitative characteristics) or an odds ratio of 1.5 (binary characteristics).

All comparisons between treatment arms will be on an intention-to-treat basis i.e. according to the group to which participants were randomised and without reference to their actual compliance with assigned treatment.

Each of the co-primary endpoints will be analysed separately in time-to-event analyses. Event rates (time to first event within each endpoint definition) will be compared between groups using a hazard ratio, 95% confidence interval and two-sided p-value from a Cox proportional hazards regression model fitted to the endpoint with censoring for non-events at their most recent study visit and a single covariate being an indicator of the group to which the individual was randomised, statin or placebo. The proportional hazards assumption will be tested for each model.

A gate-keeping procedure will be used to adjust for the multiple testing created by the presence of two co-primary endpoints. First, MACE will be tested at $\alpha=0.05$ and, if the MACE p-value is <0.05 then second, disability-free survival will be tested at $\alpha=0.05$.

Secondary analyses of the co-primary endpoints will be performed using extended Cox proportional hazards regression models based on time(s) to any event within the endpoint definition (for relevant endpoints that can occur more than once).

No statistical adjustment will be made for the multiple secondary endpoints but the reporting of all secondary endpoint analyses will make clear whether any of the co-primary endpoints were statistically significant and will state the number of secondary endpoints proposed a priori in the study protocol.

In the survival analyses, loss to follow up will be considered a censoring event. This equates to an assumption that data is missing at random given the participant's treatment group and the timing of their loss to follow up. The adequacy of this assumption will be checked in sensitivity analyses that will include both imputation approaches and adjustment for baseline covariates predictive of propensity for dropout. The analyses will be performed using commercial statistical software packages (Stata or SAS).

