6.3 Endpoint ascertainment

At 6-month telephone calls and annual visits, participants will be asked whether they have been diagnosed with any new health events which are from a list of study endpoints. Notification of a potential study endpoint will trigger the collection of further information for endpoint confirmation and adjudication. Confirmation of endpoints will be ascertained by collecting information from any of the following sources within 90 days of learning of the event:

- Details from medical records from the usual treating physician or practice held medical record.
- Medical records obtained by letter/fax/email contact with other treating specialist physicians or secondary/tertiary medical care centres.
- Case Report Forms.
- Hospital records/discharge summaries, pathology reports.
- Death Certification: The National Death Index will be routinely sourced for notification of death not identified through the above processes for up to 5 years after the completion of study.
- Review of Commonwealth Department of Health and Ageing (DOHA) database of aged care assessments (ACAP dataset).
- Review of cancer registries for up to 5 years after the completion of study.
- Aged Care Assessment Service (ACAS report): A copy is provided to the GP and assesses the needs and level of care recommended for the individual.

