Regardless of whether participants are taking study medication or not, they will still participate in study visits (clinic and/or phone calls). If participants do not want to participate in study visits (clinic and/or phone calls), they may elect to participate by review of their medical records corresponding with the trial’s duration (such as GP and hospital records) and national morbidity and mortality databases). All participants will be asked to provide approval for access to this information as part of the study enrolment procedures.

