9.2 Withdrawal

Participants will be considered to have withdrawn from the study if they revoke their consent. This means that they are not taking study medication, are not participating in study visits (clinic and/or phone calls), and that medical record review is not being conducted. All data that participants have contributed to the study up to the date of withdrawal will remain in the study database, and review of medical records dated earlier than the withdrawal date may be completed. Publicly available data such as death (e.g. from death notices) may also be used in such cases.

10. Study Medication and Supplies

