11.1 Prescription medications

All prescription medicine will be recorded on a Concomitant Medications Form including indication for use and start/stop dates. Concomitant medications will be checked at annual study visits where participants will be asked to bring in any medications/vitamins/supplements they are taking and by review of GP medical records.

12. Sample Size and Power calculations

Table 4. Sample size calculations

	ITT effect size (RR)	Power	Required number of events	Required number of participants	On treatment (true) effect
For disability free survival (Death or Dementia or Disability)	14.5%	83.1%	1,397	9,631	18%
For major adverse cardiovascular events (CV death, non-fatal MI or non-fatal stroke)	20.2%	80.0%	619	9,631	25%

Based on these sample size calculations 9,631 participants will be recruited and a total of 58,135 person-years accrued.

These calculations assume:

Loss to follow up: 2% per annum (which is expected to be conservative, i.e. the true loss to follow up is expected to be very small assuming good retention of participants and the ability to access medical records or perform record linkage for those who cease regular follow up). This translates to expecting an average of 6.04 years of follow up time per participant.

A two-sided significance level of 5% (alpha rate).

An anticipated age structure of STAREE participants of 56%: 27%: 12%: 5% in the respective age bands 70-74 years: 75-79 years: 80-84 years: 85+ years. These proportions are based on recruitment of the initial 7000 participants to the study and expectations about future recruitment.

Treatment cross-over: In year 1 of follow up we assume 8% of participants who have been randomised to statin will cease taking their study medication. Thereafter, we assume 3% of participants per annum in the statin group will cease taking study medication. In year 1 of follow up we assume 1% of participants in the placebo group will commence statin. Thereafter we assume 3% of participants per annum in the placebo group will commence statin therapy. Further we assume that there are no subsequent treatment "re-cross-overs", i.e. assume a worst-case scenario for the hazard ratio that will be observed in the intention to treat analysis.

The following event rates:

Death, dementia or persistent disability (disability-free survival) - co-primary endpoint A

All cause death

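### Event-free participants are censored at the last study visit, but events found later in records and registries are not excluded, so event time and event-free time can end on different dates

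*Protocol*

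**What the plan says.** Section 14.3 (Data analysis) specifies a Cox model for time to first event for each co-primary endpoint, with "censoring for non-events at their most recent study visit". It adds that "In the survival analyses, loss to follow up will be considered a censoring event", and plans sensitivity analyses by imputation and by "adjustment for baseline covariates predictive of propensity for dropout".

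Other sections provide for finding events without visits:

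- Section 6.3 (Endpoint ascertainment) lists GP and hospital records, aged-care and cancer databases, and states that "The National Death Index will be routinely sourced for notification of death not identified through the above processes".
- Section 9.1 says of people who want neither clinic visits nor calls that "they may elect to participate by review of their medical records" and national databases. This is a level of participation, not loss to follow-up.
- Section 9.2, on withdrawn consent, says "Publicly available data such as death (e.g. from death notices) may also be used in such cases".
- Section 12 assumes "Loss to follow up: 2% per annum" and calls this conservative, partly because of "the ability to access medical records or perform record linkage for those who cease regular follow up".

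No section says that an event counts only if it precedes the last visit. None extends the time of an event-free participant to the end of record or registry coverage.

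**The concern.** A Cox model needs the same observation window for events and for time at risk. Take a participant who has stopped visits and calls and is followed by record review. A myocardial infarction three years later can be found and counted. Three years known from the same records to be event-free are discarded. After the last contact, that person can enter the analysis only by having an event, so the censoring date depends on the outcome.

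This happens even when drop-out has nothing to do with prognosis. The planned imputation and covariate adjustment address the missing-at-random assumption and leave the two windows unequal.

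MACE is tested first in the gate-keeping procedure, so an error there also decides whether disability-free survival is tested. Inflated absolute rates could also reach the economic model, which section 5.8 bases on time-to-outcome data.

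**Working it through.** **1. The plan's own figures.** Section 12 gives MACE rates of 9.5, 11.5, 18.5 and 24.5 per 1000 person-years and an age mix of 56/27/12/5%.

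- Weighted rate: 0.56×9.5 + 0.27×11.5 + 0.12×18.5 + 0.05×24.5 = 11.87 per 1000.
- Mean follow-up: 58,135 / 9,631 = 6.04 years.
- Expected events: 11.87/1000 × 58,135 × (1 + 0.798)/2 = 620, against 619 stated.
- Required events (Schoenfeld): 4 × (1.960 + 0.842)² / (ln 0.798)² = 617, against 619 stated.

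The plan's MACE figures reproduce, so its rate and follow-up are used below.

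**2. Assumptions that the protocol does not supply.** Visit drop-out is taken as constant and unrelated to risk, at d = 2%, 3% or 4% per year. The 2% in section 12 is total loss to follow-up and is not split by arm; it is only a convenient anchor. A share f of events after the last contact is found: all, half or one fifth. One fifth is roughly what death linkage alone could reach, since section 12 puts non-fatal infarction, non-fatal stroke and cardiovascular death at 2:2:1.

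**3. Closed form.** With T = 6.04 years, mean contact time is c = (1 − exp(−dT))/d. Events accrue over c + f(T − c), while event-free time stops at c. The rate is therefore inflated by about 1 + f(T − c)/c.

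| Drop-out per year | c (years) | Inflation, f = 1 | Inflation, f = 0.2 |
|---|---|---|---|
| 2% | 5.69 | 1.062 | 1.012 |
| 3% | 5.52 | 1.093 | 1.019 |
| 4% | 5.37 | 1.126 | 1.025 |

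The hazard-ratio factor is the ratio of the two arms' inflations. For f = 1:

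- 2% v 2%: 1.00
- 3% v 2%: 1.093/1.062 = 1.03
- 4% v 2%: 1.126/1.062 = 1.06

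For f = 0.2 the last two become 1.006 and 1.013.

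**4. Simulation with six-monthly contacts and a fitted Cox model.** Results are slightly larger, because time since the last contact is also lost.

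| Statin v placebo drop-out | HR factor, f = 1 | f = 0.5 | f = 0.2 |
|---|---|---|---|
| 2% v 2% | 1.00 | 1.00 | 1.00 |
| 3% v 2% | 1.03 | 1.016 | 1.007 |
| 4% v 2% | 1.065 | 1.035 | 1.014 |
| 2% v 3% | 0.97 | 0.985 | 0.993 |

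At 2% in both arms and f = 1, rates are inflated by about 6.5%.

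**5. Meaning for the MACE test at 619 events.** Power is Φ(½√619 × |ln HR| − 1.96).

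- Planned HR 0.798: 80%.
- Factor 1.034 (3% v 2%, f = 1): HR 0.825, power about 67%.
- Factor 1.065 (4% v 2%, f = 1): HR 0.850, power about 53%.
- Factor 1.014 (4% v 2%, f = 0.2): HR 0.809, power about 75%.

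**6. Matched windows.** When events and non-events stop at the same contact date, the simulation returns a factor of 1.00 and the true rate in every scenario.

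**The case against.** Several objections have force.

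- **Counting late events is inferred.** A reader might conclude that the protocol puts events found after the last visit into the primary model. It does not say so. Section 6.3 lists sources of information, and section 9.2 says only that later deaths may be used. Treating loss to follow-up as censoring can be read as excluding anything later, and an SAP could set a cut-off. This stands as a limit. But record-only participants under section 9.1 are not lost to follow-up, and the stated rule for non-events is one-sided.
- **Few people are exposed.** Visits may be held by phone, and sections 9.1 and 9.2 count calls among study visits. Only people who stop all contact matter. This stands.
- **Unequal drop-out is assumed.** A reader might infer that side effects would drive statin participants out of visits and so bias the hazard ratio. The protocol does not support that: those who stop tablets stay in visits (sections 8.1, 8.2, 9.1 and 13.4.2), and participants and staff are blinded. No figure by arm is given. This stands, and it is why the hazard-ratio figures are scenarios and not estimates.
- **Full capture is a worst case.** Non-fatal events depend largely on notification or agreed record review, so the low-capture column may be nearer the truth. Disability-free survival was not simulated. Its dementia and disability components rely more on assessments and should be less exposed.
- **Survival curves.** A reader might extend the point to Kaplan-Meier curves, but section 14.3 specifies none.

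**Conclusion.** The point holds as a conditional one. The censoring rule in section 14.3 and the ascertainment rules in sections 6.3, 9.1, 9.2 and 12 give different end dates for events and for event-free time. The planned sensitivity analyses do not reconcile them. If late events are counted, equal visit drop-out of 2% per year overstates MACE rates by up to about 6% and leaves the hazard ratio materially unbiased. A biased hazard ratio needs drop-out to differ by arm. The factor is then at most about 1.03 (3% v 2%) or 1.065 (4% v 2%), and about 1.01 if a fifth of later events are found. The arm with more drop-out looks worse, so the error can run either way. These sizes rest on assumed drop-out and capture. The documents do not show that the trial's hazard ratio will be biased.

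**What to change.** Amend section 14.3 as follows.

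- For each co-primary endpoint, define one end-of-ascertainment date per participant: the last date through which **all** components of that composite were ascertained. This is the last visit or call, or the end of agreed medical-record review, truncated at a common study cut-off.
- Censor non-events at that date and count events only up to it.
- Use the end date of death linkage for the all-cause death endpoint only.
- For withdrawn consent, censor at withdrawal and use later deaths only in a sensitivity analysis.

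Do not simply take the latest of all contact and linkage dates. Death linkage does not observe non-fatal infarction, stroke, dementia or disability, so carrying a composite to the linkage date credits unobserved time as event-free. In the same MACE model with one fifth of later events found, that rule understates the rate by about 5% at equal 2% drop-out. It gives hazard-ratio factors of about 0.97 (3% v 2%) and 0.95 (4% v 2%), which flatters the arm with more drop-out.

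The cost is a short change of text, one derived date per participant and endpoint, and a few late events left out of the primary analysis. No new data are needed. It should be settled before unblinding.

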14.4 Training

All STAREE staff will be trained by senior study staff and study investigators and undertake a competency assessment prior to commencing their specific role.

All Staff will be provided with background information on the rationale of the STAREE trial and the study protocol. They will also be required to familiarise themselves with the key principles of Good Clinical Practice (GCP) and will attend an accredited GCP training course.

All study activities are described in standard operating procedures (SOPs), and staff will be regularly encouraged to refer to SOPs and SOP updates for guidance.

14.4.1 Research Officers

STAREE Research Officers are responsible for and will be trained in the conduct of phone screening for potential study participants, in use of the STAREE database, booking and confirming participant visits, conducting 6 month participant phone calls and labelling and dispatch of medication, receipt of study medication and follow up missing documents for randomisation and endpoint ascertainment.

14.4.2 GP Liaison Officers

STAREE GP Liaison Officers are responsible for engaging with general practices and registering GPs as STAREE co-investigators. They will be provided with practical guidance in conducting GP practice visits to recruit GPs, in data entry, and in searching GP practice databases for potential participants.

14.4.3 Research Field Officers

STAREE Field Officers are responsible for conducting baseline screening visits and annual follow up visits with study participants. They will receive training in database entry, conducting informed consent discussions with potential participants, visit conduct and performing specific study assessments (e.g. weight, height and blood pressure measurement and taking personal and medical histories) and assessing the suitability of a participant to participate in the trial.

Field Officers will observe baseline 1 and 2 and annual visits that are being conducted by a trained Field Officer to become familiar with the visit procedures. Training in the conduct of cognitive assessments will be provided in the form of training videos, SOPs and role plays. Before Field Officers can conduct independent study visits, they will undertake specific training in cognitive assessments with a Senior Field Officer and specialist STAREE Investigator and conduct 3-6 study visits under the supervision from a Senior Field Officer.

Accreditation to perform study visits will be provided subject to satisfactory performance in both the cognitive assessment training and supervised visit conduct. To maintain accreditation, Field Officers will be required to conduct a minimum of 4 visits per month (at least 2 with cognitive assessments) and performance will be reviewed annually.

15. Study Monitoring and Auditing

Monitoring and auditing in STAREE will include monitoring of investigative sites and visit conduct by study staff. This will involve monitoring of all study documentation and activities including participant files, data quality, administrative activities and endpoint collection as detailed further in the STAREE monitoring plan.

All STAREE study sites will be monitored annually by trained STAREE clinical research Site Monitors, following GCP guidelines. Site monitoring will be undertaken at all STAREE sites to ensure that the study is being conducted according to the protocol and appropriate regulatory requirements, that protocol deviations are appropriately documented and reported, the site complies with safety regulations and that personnel at each site meet GCP obligations.

All field staff involved in the STAREE study will have their activity reviewed by the Visit Conduct Monitor. Monitoring will ensure that all visit activity is conducted in accordance with the study protocol, relevant SOPs and test administration SOPs.

Study monitors will submit written reports summarising their findings to the internal Data Monitoring Committee (DMC). Where monitoring identifies risks or issues for participant safety or trial processes, appropriate steps will be taken to remedy the issue including re-training of staff and repeat monitoring.

16. Dissemination Plan

The STAREE dissemination plan will ensure that the outputs from the research inform general practice and maximise the benefit to older people.

The key audiences for the STAREE results are:

- General practitioners
- Physicians and other health professionals/clinicians
- STAREE participants
- The general public (including community groups such as Council of the Older Australian, Probus groups etc.)
- Professional organisations (e.g. RACGP)
- Funding organisations (e.g. NHMRC, Monash University)
- Scientific and medical research communities

Representatives of these key stakeholder groups will be invited to take part in discussion of the STAREE findings in relation to current clinical practice and policy and how to best translate the research findings into recommendations for wider audiences.

Multiple channels of communication will be used to disseminate STAREE findings to the wider community. These will include the following:

- Written feedback to STAREE participants and GP co-investigators on the study results and recommendations arising from the study.
- Published academic journal articles, plain English summaries, research summaries for professional journals, newsletters, presentations, and frequently asked questions section will be made accessible on the STAREE website.
- Workshops and presentations at scientific meetings, GP conferences and community and public venues.

17. References

1. Bongaarts J. Human population growth and the demographic transition. *Philos Trans R Soc Lond B Biol Sci.* 2009;364(1532):2985-90.
4. Productivity Commission 2011, *Caring for Older Australians: Overview, Report No. 53, Final Inquiry Report, Canberra.*
